3.14.3.6. Severe Persistent Hyperglycemia Requiring Rescue Therapy

A summary of initiation of rescue therapy in response to severe, persistent hyperglycemia will be provided by treatment group.

3.14.3.7. Hypoglycemia

The following categories in accordance with the 2021 American Diabetes Association position statement on glycemic targets (ADA 2021) will be defined in the database.

Glucose Alert Value (Level 1):

- **Documented symptomatic hypoglycemia** is defined as any time a participant feels he/she is experiencing symptoms and/or signs associated with hypoglycemia, and has a blood glucose (BG) level of <70 mg/dL (<3.9 mmol/L) and ≥54 mg/dL (≥3.0 mmol/L).
- **Documented asymptomatic hypoglycemia** is defined as any event not accompanied by typical symptoms of hypoglycemia, but with a measured BG <70 mg/dL (<3.9 mmol/L) and $\ge54 \text{ mg/dL}$ ($\ge3.0 \text{ mmol/L}$).
- **Documented unspecified hypoglycemia** is defined as any event with no information about symptoms of hypoglycemia available, but with a measured BG <70 mg/dL (<3.9 mmol/L) and ≥54 mg/dL (≥3.0 mmol/L).

Documented Clinically Significant Hypoglycemia (Level 2):

- **Documented symptomatic hypoglycemia** is defined as any time a participant feels he/she is experiencing symptoms and/or signs associated with hypoglycemia and has a BG level of <54 mg/dL (<3.0 mmol/L).
- **Documented asymptomatic hypoglycemia** is defined as any event not accompanied by typical symptoms of hypoglycemia but with a measured BG <54 mg/dL (<3.0 mmol/L).
- **Documented unspecified hypoglycemia** is defined as any event with no information about symptoms of hypoglycemia available but with a measured BG <54 mg/dL (<3.0 mmol/L).

Severe Hypoglycemia (Level 3):

Severe hypoglycemia is defined as an episode with severe cognitive impairment requiring the assistance of another person to actively administer carbohydrate, glucagon, or other resuscitative actions. These episodes may be associated with sufficient neuroglycopenia to induce seizure or coma. Plasma glucose (PG) measurements may not be available during such an event, but neurological recovery attributable to the restoration of PG to normal is considered sufficient evidence that the event was induced by a low PG concentration.

Other hypoglycemia categories:

Nocturnal hypoglycemia is defined as any hypoglycemic event that occurs between bedtime and waking. If a hypoglycemic event meets the criteria of severe, the event would specifically be collected as an SAE. Serious hypoglycemia is defined by pharmacovigilance criteria and will also be captured with an SAE form.

To avoid duplicate reporting, all consecutive hypoglycemic events occurring within a 1-hour period will be considered as a single hypoglycemic event.

Hypoglycemia data will be censored at the time of receipt of new antihyperglycemic medication. This censoring will occur regardless of whether the reason for the alternative medication is rescue from severe, persistent hyperglycemia (with or without continuation of assigned study medication) or maintenance of glucose control in the event of cessation of assigned study medication.

Both the incidence (percent of participants experiencing ≥1 episode) and the rate (episodes/participant/year) of level 2 or level 3 hypoglycemia will be reported.

[figure not shown]
A listing of level 2 or 3 hypoglycemia will also be provided.

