6.5. Concomitant Therapy

Any medication or vaccine (including over-the-counter or prescription medicines, vitamins, and/or herbal supplements) or other specific categories of interest that the participant is receiving at the time of enrollment or receives during the study must be recorded along with:

- Reason for use
- Dates of administration including start and end dates
- Dosage information including dose and frequency for concomitant therapy of special interest (drugs used for diabetes, diuretics, drugs used for obesity, and cardiovascular drugs)

The sponsor should be contacted if there are any questions regarding concomitant or prior therapy.

Initial doses of tirzepatide delay gastric emptying and have the potential to transiently impact the rate of absorption of concomitantly administered oral medicinal products. Tirzepatide should be used with caution in participants receiving oral medicinal products that require rapid GI absorption following the initial doses of tirzepatide, as exposure to oral medications may be increased.

Prevention of Hypoglycemia

Similar to GLP-1 RAs, tirzepatide does not generally cause hypoglycemia, but it is recommended to decrease the dose of concomitant sulfonylurea or insulin to reduce the risk of hypoglycemic episodes in patients with T2DM. For participants with T2DM, specific, individually tailored adjustments of the respective antihyperglycemic medications should be considered during the entire study.

At Visit 2, with the initiation of study drug, the dose adjustments to the following concomitant glucose lowering medications are recommended.

Sulfonylureas: Sulfonylurea dose is recommended to be reduced at least 50% or discontinued, especially if the participant is receiving a low dose at randomization.

Insulins: For participants on basal insulin and with screening HbA1c \leq 8.5%, the daily dose is recommended to be reduced by at least 20%.

During the dose escalation period, consider adjusting the total daily dose of insulin, if required for controlling worsening hyperglycemia and its acute complications.

During the maintenance period, further insulin dose reduction for the prevention of hypoglycemia is to be considered at the investigator's discretion.

Standard of Care for T2DM

The standard of care for diabetes may be adjusted at the discretion of the investigator as clinically indicated in accordance with local standard of care and professional society guidelines.

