In addition, if HbA1c is >9.0% at Week 12 or >8.0% at Week 24 or later in the study, glucose-lowering therapy should be adjusted to improve glycemic control as outlined above. In the event a participant's HbA1c values are less than these thresholds but are higher than what the investigator feels comfortable leaving untreated, glucose-lowering medication can be adjusted. In addition, if participants develop symptoms of hyperglycemia (for example, polyuria and polydipsia), the investigator should implement measures to determine glycemic control and adjust as necessary. For participants newly diagnosed with T2DM during the trial, appropriate glucose-lowering therapy should be initiated per standard of care.

Standard of Care for Heart Failure

Anticipated treatment for heart failure should be decided prior to randomization.

Both American College of Cardiology/American Heart Association and European Society of Cardiology guidelines recommend symptom management with diuretic agents in patients with excess volume, as well as aggressive risk factor management for comorbidities for the treatment of HFpEF (van der Meer JACC 2019). Optimization of volume status and proactive adjustment of diuretic doses will help control symptoms and volume overload.

Participants should remain on stable doses of medications to treat heart failure condition and comorbidities such as hypertension. With the exception of diuretics, dose modification or alteration of such background therapies should be avoided unless all other measures fail to improve the participant's condition. However, if the participant's condition warrants a change in any of these medications, it will be allowed at the discretion of the investigator.

Management of Participants with Gastrointestinal Symptoms

In the Phase 2 program, the most commonly reported TEAEs for participants receiving tirzepatide were nausea, vomiting, and diarrhea. To mitigate GI symptoms and manage participants with intolerable GI AEs, the investigator should:

- Advise participants to eat smaller meals, for example, splitting 3 daily meals into 4, or more smaller meals, and to stop eating when they feel full. Also, participants may be informed that lower-fat meals could be better tolerated.
- Prescribe symptomatic medication (for example, anti-emetic or antidiarrheal medication) per local country availability and individual participant needs. Use of symptomatic medication should be captured as concomitant medication in the eCRF.

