9.4.5. Other Safety Analyses

Safety will be assessed by summarizing and analyzing AEs, special safety topics, laboratory analytes, and vital signs. All safety analyses will be made on the Safety Population. Unless specified otherwise, all data obtained during study period from Safety Population, regardless of adherence to study drug, will be used for safety analyses. The details for safety analysis will be described in the SAP.

Adverse events will be coded from the actual term using MedDRA and reported with preferred terms and system organ class.

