3.14. Safety Analyses

Unless specified otherwise, safety analyses will be conducted in the safety population (Table GPID.3.1). All events that occur between the first dose date of study drug and the end date of follow-up will be included in the safety analyses, regardless of the adherence to study drug.

The statistical assessment of homogeneity of the distribution of categorical safety responses between tirzepatide MTD and placebo will be conducted using Fisher's exact test, unless specified otherwise. Risk difference and its 95% CI will also be provided, where appropriate.

The mean change from baseline differences among treatments at all scheduled visits will be assessed via an MMRM analyses using REML. Unless specified otherwise, the MMRM analysis will contain measurements from planned visits up to 104 weeks, and the model will include treatment group, stratification factors, visit and treatment-by-visit interaction as fixed effects, and baseline value of the safety parameter as a covariate. To model the covariance structure within participants, the unstructured covariance matrix will be used. If this model fails to converge, the covariance structures specified in Section 3.13.1.4 will be tested in order until convergence has been met. If the data does not warrant the MMRM model, then an ANCOVA model will be conducted.

For selected safety parameters, a time-to-first-event analysis via the Cox-proportional hazards model may be conducted. Participants without the event will be censored at the end of follow-up.

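### Hypoglycemia incidence is a crude percent although the data are cut at a new antihyperglycemic drug, so it under-counts whichever arm starts more such drugs

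*SAP*

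**What the plan says.** SAP 3.14.3.7 sets the rule: "Hypoglycemia data will be censored at the time of receipt of new antihyperglycemic medication". It applies whether the drug was given as rescue from severe persistent hyperglycemia, with or without continued study drug, or for "maintenance of glucose control in the event of cessation of assigned study medication".

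The same section then names the summaries: "Both the incidence (percent of participants experiencing ≥1 episode) and the rate (episodes/participant/year) of level 2 or level 3 hypoglycemia will be reported". It also plans a listing of level 2 and 3 episodes. It does not say which denominator the percent uses, whether the person-years in the rate end at the censoring date, or whether the listing is censored.

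The general rule in SAP 3.14 is wider: "All events that occur between the first dose date of study drug and the end date of follow-up will be included" in the safety analyses. Protocol 9.4.5 is similar: "all data obtained during study period from Safety Population, regardless of adherence to study drug, will be used for safety analyses". Both sentences allow exceptions, and 3.14.3.7 is one. For categorical safety responses, SAP 3.14 says the between-arm comparison "will be conducted using Fisher's exact test, unless specified otherwise". A Cox analysis of time to first event is optional there, for selected parameters, and hypoglycemia is not named.

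**The concern.** Censoring removes episodes from the numerator of the percent but removes nobody from its denominator. A participant who starts a new drug at Week 12 without an earlier episode is counted exactly like one who was followed to the end of the study without an episode. This is harmless only if both arms start new drugs to the same extent.

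Unequal starts are plausible. Protocol 6.5 advises a cut in background therapy at Visit 2 in both arms, under the blind; for example, "Sulfonylurea dose is recommended to be reduced at least 50% or discontinued". Later, "if HbA1c is >9.0% at Week 12 or >8.0% at Week 24 or later in the study, glucose-lowering therapy should be adjusted". One arm receives a drug that, by Protocol 4.3, improved glycemic control over an active comparator in Phase 2. More added drugs would therefore be expected on placebo. This is an inference: no start rates are given, and the second trigger, loss of study drug, could add censoring on tirzepatide.

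At stake is a between-arm safety comparison that can differ from zero with no difference in hazard, and the loss of some episodes from every planned summary table.

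**Working it through.** The plan states no hypoglycemia rate, start rate or power for this analysis, so there is no planned figure to reproduce. What follows is an illustration.

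**Inputs from the documents**
- About 350 participants per arm (Protocol 1.1).
- 40% to 50% with T2DM (Protocol 2.2). The midpoint gives 0.45 × 350 = about 157 per arm.
- Treatment of at least 52 weeks, and maximum participation of about 120 weeks (Protocol 4.1).

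**Assumed inputs**
- Hazard h of a first level 2/3 episode, equal in both arms: 0.10 per year (range 0.05 to 0.20).
- Share p that starts a new drug by time T: placebo 20%, tirzepatide 5% (range 10% vs 2% to 30% vs 10%).
- T = 1.5 years.
- Constant hazards, so the start rate is r = −ln(1 − p)/T.

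**Crude percent under the SAP rule:** h/(h + r) × [1 − exp(−(h + r)T)]
- Placebo: r = 0.223/1.5 = 0.1488. Then 0.10/0.2488 × [1 − exp(−0.3731)] = 0.4020 × 0.3114 = 12.52%.
- Tirzepatide: r = 0.0513/1.5 = 0.0342. Then 0.10/0.1342 × [1 − exp(−0.2013)] = 0.7452 × 0.1823 = 13.59%.
- Difference: +1.07 points against tirzepatide, or about 1.7 of 157 participants.

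**Incidence had no new drug been started:** 1 − exp(−0.15) = 13.93% in both arms. The crude percent therefore misses about 10% of this on placebo (12.52/13.93 = 0.90) and about 2.5% on tirzepatide (13.59/13.93 = 0.976). A Kaplan-Meier estimate that censors at the new drug recovers 13.93% in both arms, provided that censoring is independent of the hypoglycemia hazard.

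**Range of the spurious difference**

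| h per year | New drug, placebo vs tirzepatide | Difference (points) |
|---|---|---|
| 0.05 | 10% vs 2% | +0.29 |
| 0.10 | 20% vs 5% | +1.07 |
| 0.10 | 15% vs 15% | 0 |
| 0.20 | 30% vs 10% | +2.67 |

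**A second model agrees.** Take a full-follow-up incidence of 10%, so h = −ln(0.9) over one unit of follow-up, and start times uniform over follow-up. A starter then has an observed incidence of 1 − 0.1/0.10536 = 5.09%. With starts of 20% and 3%, placebo shows 0.80 × 10% + 0.20 × 5.09% = 9.02%, and tirzepatide 0.97 × 10% + 0.03 × 5.09% = 9.85%. The apparent risk ratio is 1.09 and the true ratio is 1.00.

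**Rate per participant-year** (main case)
- Person-time cut at the new drug: 0.100 in both arms, so no distortion.
- Full person-time: mean counted time is p/r, so the observed rate is h × p/(rT). Placebo: 0.10 × 0.20/0.2231 = 0.090. Tirzepatide: 0.10 × 0.05/0.0513 = 0.098. The distortion is of the same kind as in the crude percent.

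**All episodes counted** (main case)
- If the added drug leaves the hazard unchanged: 13.93% in both arms.
- If it doubles the hazard: 15.20% on placebo and 14.24% on tirzepatide, a difference of −0.96 points. The sign reverses.

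**Where the cut episodes still appear.** Severe episodes are reported as SAEs (Protocol 10.5.1.1, SAP 3.14.3.7). They are then tabulated and listed under SAP 3.14.1.4 and narrated under 3.14.2, with no such censoring stated. Non-severe episodes go on a dedicated form and are not otherwise recorded as AEs (Protocol 10.5.1.1). A level 2 episode after censoring that is neither severe nor serious therefore reaches no other planned summary table.

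**The case against.** The best defence is that the rule answers a legitimate question: how much hypoglycemia occurs on assigned treatment before anything else is added. For that question the crude percent is a valid description. Counting all episodes is not neutral either. Rescue may include basal and prandial insulin (Protocol 6.5), so an all-events table loads rescue-drug hypoglycemia onto the arm that is rescued more, as the reversal to −0.96 points shows. This stands, and it is why the all-events version should not become the main analysis. It does not save the crude percent as a between-arm comparison, because the SAP names no such estimand and the default test ignores observed time.

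Second, the SAP censors data, not only events, and elsewhere it ends observed time at censoring (SAP 3.2, 3.13.1.2.1.2). Cutting the person-time is then the natural reading of the rate. I agree; it needs one sentence to make it explicit.

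Third, the assumed start rates may be high. Rescue needs confirmed, sustained fasting glucose above set thresholds, HbA1c of 9.5% or more was excluded in participants with T2DM, and an adjustment of therapy may be a dose change and not a new drug. This limits the size of the effect, not its existence.

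Fourth, imbalance will be partly visible. SAP 3.14.3.6 summarizes rescue by arm, and SAP 3.10 summarizes post-randomization changes in antihyperglycemic therapy. Neither gives the number censored in this analysis.

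**Conclusion.** The defect is confined to the crude percent of level 2/3 hypoglycemia and the Fisher's exact test that applies to it by default. Under equal hazards it under-counts the arm with more new-drug starts. The main illustration gives about 1 percentage point, with a range of +0.29 to +2.67 points over the unequal-start cases examined. All of this rests on assumed hazards and start rates, and it vanishes if starts are balanced. A separate gap is that level 2 episodes after censoring have no other summary table.

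A reader might infer more, and the documents do not support it:
- **That every hypoglycemia comparison is biased.** Under equal hazards the rate is not, if person-time stops at censoring.
- **That severe episodes on tirzepatide plus an added drug vanish.** They stay in the SAE tables, listing and narratives.
- **That the rule hides a tirzepatide risk in the comparison.** If placebo is censored more, the crude percent makes tirzepatide look worse.
- **That the SAP breaks the general safety rule.** SAP 3.14 and Protocol 9.4.5 both permit exceptions.
- **That an SGLT2 inhibitor started for heart failure triggers censoring.** The sentence that explains the rule names only glycemic reasons, so this reading is strained.

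This is a cheap improvement, not a flaw that threatens the trial's conclusions.

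**What to change.** Keep the censored analysis and amend SAP 3.14.3.7 as follows.

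1. Replace or accompany the crude percent with a Kaplan-Meier or cumulative-incidence estimate of time to first level 2/3 episode. Treat the new drug as censoring. Treating it as a competing event would return the same quantity as the crude percent. Note the assumption of independent censoring.
2. State that person-time for the rate ends at the censoring date.
3. State the denominator (Safety Population or participants with T2DM), and report the number censored per arm.
4. Add a supportive table of incidence and rate that counts all episodes from first dose to end of follow-up, and leave the listing uncensored.

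The cost is SAP wording and one extra table; no new data are needed. The all-events figures also reflect hypoglycemia caused by the added drugs, so they should be read beside the censored result and not replace it.

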- c Telephone visits can become office visits. Site documentation will serve as the source for telephone visits. Additional, optional telephone visits may be conducted at investigator discretion. If patient requires study drug at a telephone visit, the participant will need to come to the clinic to pick up study drug in addition to telephone visit.
- d Perform at ET only if participant early terminates at or prior to Week 52.
- e Two 6MWTs conducted at screening visit.
- f See Section 10.10.1 to determine if the 6MWT needs to be repeated for Visit 2.
- g This includes glucose monitoring for participants with T2D, weekly study drug injection.
- h Perform PRO at ET only if participant early terminates at or prior to Week 52.
- i Unscheduled Visits: laboratory tests may be drawn according to investigator discretion. If only re-test labs required, site is not required to complete an unscheduled visit and associated procedures.
- Required at Visit 2 randomization if screening labs are older than 28 days for chemistry, lipid, and pancreatic lipase/amylase.
- k Collect serum pregnancy at Visit 2 only if Visit 1 serum was ≥28 days prior.
- 1 Only collect calculated eGFR with Clinical Chemistry sample if screening labs are older than 28 days.

2. Introduction

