12 patients in the placebo group, but only in 1 patient in the semaglutide group (HR 0.08; 95% CI 0.00 to 0.42)

It has been demonstrated that tirzepatide can provide significant body weight loss and improvement of lipid and glucose metabolism in patients with and without T2DM (Frias et al. 2018; Wilson et al. 2020; Jastreboff et al. 2022). It is known that the body weight reduction with GLP-1 RAs in patients without T2DM is higher than in patients with T2DM (Davies et al. 2015; Pi-Sunyer et al. 2015; Lingvay et al. 2018). If Study GPID is assumed to include 40% to 50% of patients with T2DM, the mean placebo-adjusted body weight percent reduction that tirzepatide can provide in 52 weeks in this study is estimated to be 15% to 16%. This is based on tirzepatide clinical data and the understanding of body weight loss differences between patients with and without T2DM treated with GLP-1 RAs. Thus, the predicted body weight loss with treatment with tirzepatide is close to that shown with bariatric surgery.

Tirzepatide may provide benefit to patients with HFpEF and obesity by virtue of cardiometabolic improvements (Wilson et al. 2020). Given the wide distribution of GIP receptor in the adipose tissue, GIP is thought to be actively involved in lipid and glucose metabolism. As suggested by the results of emerging data (Kosiborod et al. 2023) and the significant weight loss achieved with tirzepatide, the effect of tirzepatide on HF events in an obesity-related HFpEF population are expected to be robust. Therefore, it will be meaningful to assess the impact of tirzepatide not only on functional and symptomatic endpoints but also on the reduction in the risk of HF events in SUMMIT, thereby facilitating the holistic understanding of the clinical impact of tirzepatide treatment in patients with HFpEF and obesity.

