10.5.1. Special Safety Topics

10.5.1.1. Hypoglycemia

Upon ICF signing, all participants will be educated about signs and symptoms of hypoglycemia, how to treat hypoglycemia, and how to collect appropriate information for each episode of hypoglycemia.

Hypoglycemia may be identified by spontaneous reporting of symptoms from participants (whether confirmed or unconfirmed by simultaneous glucose values) or by BG samples collected during study visits.

All participants with T2DM and who develop diabetes during the study will be provided with glucometers.

Participants with T2DM will be provided a diary to record relevant information (for example, glucose values, symptoms).

All hypoglycemic episodes are to be recorded on a specific eCRF and should not be otherwise recorded as AEs unless the event meets severe criteria. If a hypoglycemic event meets severe criteria (see definition below), it should be recorded as serious on the AE eCRFs, and reported to the sponsor as an SAE. To avoid duplicate reporting, all consecutive BG values <70 mg/dL (<3.9 mmol/L) occurring within a 1-hour period may be considered to be a single hypoglycemic event (Weinberg et al. 2010; Danne et al. 2013).

Investigators should use the following definitions and criteria when diagnosing and categorizing an episode considered to be related to hypoglycemia (the BG values in this section refer to values determined by a laboratory or International Federation of Clinical Chemistry and Laboratory Medicine blood-equivalent glucose meters and strips) in accordance with the 2020 American Diabetes Association position statement on glycemic targets (ADA 2020):

Glucose Alert Value (Level 1):

- Documented symptomatic hypoglycemia is defined as any time a participant feels that he or she is experiencing symptoms and/or signs associated with hypoglycemia and has a BG level of <70 mg/dL (<3.9 mmol/L).
- Documented asymptomatic hypoglycemia is defined as any event not accompanied by typical symptoms of hypoglycemia, but with a measured BG <70 mg/dL (<3.9 mmol/L).
- Documented unspecified hypoglycemia is defined as any event with no information about symptoms of hypoglycemia available, but with a measured BG <70 mg/dL (<3.9 mmol/L).

Clinically Significant Hypoglycemia (Level 2):

• Documented symptomatic hypoglycemia is defined as any time a participant feels that he or she is experiencing symptoms and/or signs associated with hypoglycemia and has a BG level of <54 mg/dL (<3.0 mmol/L).

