3.1. Populations for Analyses

The populations for analyses are defined in the following table (Table GPID.3.1).

Table GPID.3.1. Description of Analysis Populations

Analysis Population	Description	
Entered	All participants who sign the ICF.	
Randomized/ITT Population	All participants assigned to treatment, regardless of whether they take any doses of study treatment, or if they took the correct treatment. Participants will be analyzed according to the treatment group to which they were assigned.	
Safety Population	All participants in the ITT population who take at least 1 dose of study treatment. Participants will be analyzed according to the treatment group to which they were assigned.	

Abbreviations: ICF = informed consent form; ITT = intent-to-treat.

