3.15.2. Safety in Special Groups and Situations

3.15.2.1. Intrinsic Factors

A subgroup analysis will be presented for common TEAEs, for the purposes of presentation in the summary of clinical safety (SCS). The subgroups will be

- age group: $<65, \ge 65$ years
- sex: female, male
- race: American Indian or Alaska Native, Asian, Black/African American, Native Hawaiian or Other Pacific Islander, White, and Other
- BMI: ≥ 30 and ≤ 35 , ≥ 35 and ≤ 40 , ≥ 40 kg/m²
- T2DM: Yes, No, and
- eGFR: <60 mL/min/1.73m², ≥60 mL/min/1.73m².

The response variable will be each most common TEAE. The explanatory variables will be treatment, subgroup, and treatment-by-subgroup interaction. Within each subgroup category, odds ratios (treatment over placebo) and associated p-values will be provided.

An additional summary of AEs will be provided for the age groups of $<65, \ge 65$ to $<75, \ge 75$ to <85, and ≥ 85 years to meet expectations from the European Union (EMA 2014). A summary table will be created similarly to Table 12.12 in the PHUSE AE white paper (PHUSE 2017). Rows of the table include number of participants with at least 1 of the following:

- TEAE
- SAE (separate rows for fatal, hospitalization, life-threatening, disability, other)
- AEs leading to study intervention discontinuation
- Accidents and injuries (SMQ)
- Cardiac disorders (SOC)
- Infections and infestations (SOC)
- Nervous system disorders (SOC)
- Psychiatric disorders (SOC)
- Vascular disorders (SOC)
- Central nervous system vascular disorders (SMQ)
- Anticholinergic syndrome (PT),
- Fractures, or
- Hypotension, falls, fractures.

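### Level 2 and level 3 hypoglycemia are summarized without a split by T2DM, although level 2 detection depends mainly on glucometers that only participants with diabetes receive

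*SAP*

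**What the plan says.** SAP 3.14.3.7 defines three level 2 subtypes (symptomatic, asymptomatic, unspecified), each requiring a measured glucose below 54 mg/dL. Level 3 is defined clinically and can be established without a glucose value. The section then states: "Both the incidence (percent of participants experiencing ≥1 episode) and the rate (episodes/participant/year) of level 2 or level 3 hypoglycemia will be reported". It also plans a listing of these events and censors hypoglycemia data when a new antihyperglycemic drug is received. It names neither a denominator nor a split by diabetes status.

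The denominator therefore comes from SAP 3.14: "Unless specified otherwise, safety analyses will be conducted in the safety population". SAP 3.1 defines that population as "All participants in the ITT population who take at least 1 dose of study treatment", which includes participants with and without T2DM.

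On ascertainment, Protocol 10.5.1.1 says: "All participants with T2DM and who develop diabetes during the study will be provided with glucometers". It gives the diary for glucose values and symptoms to participants with T2DM. Footnote g of the Schedule of Activities, on the diary and compliance check, reads: "This includes glucose monitoring for participants with T2D, weekly study drug injection". For everyone, Protocol 10.5.1.1 also allows detection through spontaneous symptom reports and glucose samples taken at study visits.

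The one planned safety subgroup analysis that includes T2DM is in SAP 3.15.2.1: "A subgroup analysis will be presented for common TEAEs". Protocol 10.5.1.1 sends hypoglycemic episodes to a dedicated eCRF and keeps non-severe ones out of the adverse event record.

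**The concern.** The summary pools two groups that differ in how closely glucose is watched and in background risk. Protocol 6.5 links hypoglycemia risk to concomitant sulfonylurea or insulin in patients with T2DM. In participants without T2DM, a low level 2 count partly reflects few measurements.

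A pooled percentage, rate or risk difference then describes neither group well. It understates the absolute risk where glucose is monitored. It also gives the less-monitored group an apparently low risk that the data can support only weakly.

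No other planned table supplies the split. The T2DM subgroup table covers common TEAEs, which SAP 3.14.1.2 sets at 5% or more of participants, and non-severe hypoglycemia is not recorded as an adverse event. The subgroup list in SAP 3.15.1 is for efficacy. The planned listing shows cases but no stratum denominators or person-time.

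**Working it through.** The documents give no expected hypoglycemia incidence or rate, so there is no stated figure to reproduce. The question is how far a pooled summary can fall below the T2DM figure.

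**Inputs from the documents**
- T2DM share p: Protocol 2.2, "If Study GPID is assumed to include 40% to 50% of patients with T2DM". This is a planning assumption made to predict weight loss, not a quota or an observed share.
- About 350 participants per arm (Protocol 1.1), so 350 × 0.40 = 140 to 350 × 0.50 = 175 per arm with T2DM.
- Randomization is stratified by diagnosed T2DM (Protocol 6.3).
- Clinical chemistry with glucose is scheduled for all participants at Weeks 12, 24 and 52 in the first year after randomization (Schedule of Activities).

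**Assumptions, shown as ranges**
- r: detected incidence without T2DM divided by incidence with T2DM.
- t: mean person-time with T2DM divided by that without.

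**Incidence.** The pooled incidence is the T2DM incidence times [p + (1 − p)r], so the understatement factor is 1/[p + (1 − p)r].

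| r | p = 0.40 | p = 0.50 |
|---|---|---|
| 0 | 1/0.40 = 2.50 | 1/0.50 = 2.00 |
| 0.10 | 1/0.46 = 2.17 | 1/0.55 = 1.82 |
| 0.25 | 1/0.55 = 1.82 | 1/0.625 = 1.60 |
| 0.50 | 1/0.70 = 1.43 | 1/0.75 = 1.33 |

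For a given share, r = 0 gives the largest factor. As an illustration, a T2DM incidence of 10% with r = 0 would appear as 4% to 5% pooled.

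**Between-arm contrast.** Suppose 10% versus 5% in T2DM (illustrative), r = 0 and T2DM balanced between arms. The risk difference of 5 points becomes 0.40 × 5 = 2.0 to 0.50 × 5 = 2.5 points. The risk ratio is (p × 10)/(p × 5) = 2.0, unchanged. With the same r above zero in both arms, the bracketed term cancels from the ratio and the risk difference shrinks by the factor in the table.

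**Rate.** With r = 0 (no detected episodes outside T2DM), the factor is (pt + 1 − p)/(pt). At t = 1 it is again 2.5 to 2.0. Censoring at a new antihyperglycemic drug would mainly shorten person-time in T2DM, so t may be below 1. At t = 0.8 the factor is 0.92/0.32 = 2.875 for p = 0.40 and 0.90/0.40 = 2.25 for p = 0.50. The rate factor can therefore exceed 2.5.

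**The case against.** The trial enrolls people with HFpEF and obesity, with or without T2DM, so incidence per treated participant in that whole population is a legitimate quantity. Randomization is stratified by T2DM, a listing is planned, SAP 3.2 allows additional analyses, and no hypothesis test depends on this summary. All of this stands. It is why the pooled row should stay and why the point concerns absolute figures. It does not supply a prespecified split.

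A reader might also infer four stronger things that the documents do not support.

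- *That participants without T2DM are not measured.* They have scheduled visit glucose samples, can report symptoms, are educated about hypoglycemia like everyone else, and receive a glucometer if they develop diabetes. They are measured less often.
- *That level 3 events are missed in the same way.* Level 3 needs no glucose value and is reported as an SAE for any participant. The detection argument is confined to level 2; for level 3 only the difference in background risk remains.
- *That the treatment comparison is distorted.* The ratio between arms is largely preserved; the absolute incidence, rate and risk difference are what shrink.
- *That the SAP expressly chooses the whole population here.* It does not; that follows from the SAP 3.14 default.

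**Conclusion.** The point holds as a gap in the planned safety display. Followed as written, the SAP gives a pooled level 2 or 3 incidence and rate, with no T2DM-specific summary anywhere else.

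The understatement of absolute incidence and risk difference relative to T2DM is up to about 2- to 2.5-fold. A reader might take that as the expected size, but it is a ceiling for incidence at the assumed shares. It requires that no events be detected outside T2DM and that the enrolled T2DM share match the 40% to 50% planning figure. At a non-T2DM incidence of 10% to 25% of the T2DM value, the factor is about 1.6 to 2.2; at half, it is 1.3 to 1.4. These ratios are assumptions, and the risk-difference result further assumes that the ratio is similar in both arms. For the rate, no single factor applies because person-time differs with censoring.

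No primary or key secondary conclusion is affected.

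**What to change.** In SAP 3.14.3.7, name the safety population as the analysis set. Report incidence, rate and risk difference for level 2 and for level 3 hypoglycemia, each separately for participants with and without diagnosed T2DM at baseline, next to the whole-population row. State that person-time for the rate ends at the censoring date.

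The cost is SAP wording and one table split on a randomization stratum that is already collected. No new data are needed, and clinical conduct does not change.
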